22. Unstable asthma within 3 months of randomization or symptomatic asthma on the day of vaccination as assessed by the site investigator
23. Have past or current medical problems or findings from physical exam or laboratory testing not listed above, which in the opinion of the investigator, may pose additional risks from participation in the study or which may interfere with the ability to comply with study requirements. This includes individuals with underlying conditions or other medications that, in the opinion of the investigator, may increase risk in the event of an anaphylactic reaction or lead to complications following administration of epinephrine.

Premature Discontinuation of Investigational Agent	
Vaccination will be prematurely discontinued for any participant for any of the following reasons:
 
 Participant has a CoFAR Grade 2 or higher systemic allergic reaction regardless of tryptase, or a CoFAR Grade 1 reaction with elevated tryptase [1.2 x baseline plus 2 ng/ml] that is at least possibly related to the first dose of vaccine. If the systemic allergic reaction took place after the participant has left the vaccination clinic and no tryptase measurements are available, Grade 1 events will not constitute criteria for discontinuation, but counseling by a study physician will be required. The investigator believes that it is no longer in the best interest of the participant to receive the second vaccination.
Study Stopping Rules	
Study enrollment will be suspended and vaccinations will be put on hold pending Data and Safety Monitoring Board (DSMB) expedited review of all pertinent data in the event of any one of the following:
 
 One Grade 4 or higher adverse event (AE) that is at least possibly related to the vaccine Five participants in the first 100 HA/MCD participants vaccinated or 5% of HA/MCD participants thereafter experience a Grade 3 systemic allergic reaction at least possibly related to the vaccine

2. INTRODUCTION

This statistical analysis plan includes pre-planned analyses related to the study objectives outlined in the protocol.

3. GENERAL ANALYSIS AND REPORTING CONVENTIONS

The following analyses and reporting conventions will be used:

- Categorical variables will be summarized using counts (n) and percentages (%) and will be presented in the form “n (%).” Percentages will be rounded to one decimal place.
- Numeric variables will be summarized using n, mean, standard deviation (SD), median, minimum (min), maximum (max). The min/max will be reported at the same level of significance as original data. The mean and median will be reported at one more significant digit than the precision of the data, and SD will be reported at two more significant digits than the precision of the data.
- The median will be reported as the average of the two middle numbers if the dataset contains an even number of observations.
- Test statistics including *t* and *z* test statistics will be reported to two decimal places.
- P*-values will be reported to three decimal places if greater than or equal to 0.001. If less than 0.001, the value will be reported as “<0.001.” A *p*-value can be reported as “1.000”

only if it is exactly 1.000 without rounding. A *p*-value can be reported as “0.000” only if it is exactly 0.000 without rounding.

If departures from these general conventions are present in the specific evaluations section of this SAP, then those conventions will take precedence over these general conventions.

4. ANALYSIS SAMPLES

As-treated sample: All participants who are randomized and receive at least one active vaccination for any active injection analysis or all participants who are randomized and receive a placebo for any placebo injection analysis. Participants will be analyzed according to the vaccine they received.

Per-Protocol sample: All participants who are randomized and receive all assigned vaccination doses. Participants who do not receive a second active vaccination due to experiencing an allergic reaction will be included in the analysis. Participants will be analyzed according to the vaccine they received.

Safety sample: All participants who consent and undergo screening procedures. Participants will be analyzed according to the vaccine they actually received, regardless of the treatment arm to which they were randomized. Non-treatment emergent adverse events (e.g., any adverse event that occurs before the first injection) will be summarized in all participants in the safety sample, while treatment-emergent adverse events (e.g., any adverse event that occurs on or after the first injection) will be summarized in the subset of participants who receive an injection (placebo or active vaccination).

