The primary endpoint for this trial is the rate of systemic allergic reactions defined by the [Consortium for Food Allergy Research \(CoFAR\) Grading Scale](#) (Grade 2 or higher regardless of serum tryptase level or Grade 1 with elevated serum tryptase levels). This endpoint was chosen for several reasons: 1) The CoFAR Grading Scale was developed by specialists with extensive experience in systemic allergic reactions and in anaphylaxis and has proven to be a reliable system for assessing and recording reactions in multiple National Institute of Allergy and Infectious Diseases (NIAID) funded studies; 2) Because the study will be conducted under the supervision of an allergist at each site, it is unlikely that any participants will develop severe anaphylaxis, since they will be promptly treated to prevent such an outcome; and 3) Recognition, recording, and grading of all systemic allergic reactions is of importance as mild reactions induced by the first vaccine dose may constitute risk factors for more severe reactions after the second dose.

Epidemiologic studies, including the current CDC investigations into the anaphylactic responses to these vaccines, use the Brighton Collaboration Criteria. These criteria will be used as a secondary endpoint in this study to allow comparisons with publications that rely on those criteria.

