### **6.5. Premature Discontinuation of Investigational Agent**

Vaccination will be prematurely discontinued for any participant for any of the following reasons:

- Participant has a CoFAR Grade 2 or higher systemic allergic reaction regardless of tryptase, or a CoFAR Grade 1 reaction with elevated tryptase [1.2 x baseline plus 2 ng/ml] that is at least possibly related to the first dose of the vaccine. If the systemic allergic reaction took place after the participant has left the vaccination clinic and no tryptase measurements are available, Grade 1 events will not constitute criteria for discontinuation, but counseling by a study physician will be required (see below).
- The investigator believes that it is no longer in the best interest of the participant to receive the second vaccination

In the above cases, the participant will be asked to return for his/her next in clinic study visit during which reactogenicity symptoms will be reviewed (electronic diary review or return and review of paper diary), adverse events (AEs) and concomitant medications will be recorded, and pre-vaccination biospecimens will be obtained per protocol.

Vaccination may be prematurely discontinued for any participant for any of the following reasons:

- If a participant has a Grade 1 (per [CoFAR Grading Scale](#)) systemic allergic reaction with no evidence of systemic mast cell activation to the first dose of either the Pfizer-BioNTech COVID-19 Vaccine or Moderna COVID-19 Vaccine, he/she will receive counseling by a study physician and will be allowed to receive a second dose if he/she so chooses.
- Because the placebo will consist of a normal saline injection, a reaction to placebo will not require termination from subsequent active vaccination, if the participant is willing to proceed following counseling.
- If a participant becomes pregnant between the first and second doses of vaccine, she will receive counseling by a study physician and will be allowed to receive a second dose if she so chooses.

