#### 14.7. Sample Size Considerations

The within vaccine sample size of 1700 participants, 1020 in the HA/MCD population and 680 in the comparison population was determined to detect a minimum proportion difference between the two populations of approximately 0.01 with at least 80% power, assuming a two-sided unconditional exact test. The proportion is assumed to be 0.0001 (1/10,000) in the comparison group and 0.01 (1/100) in the HA/MCD group (see [Table 14.7](#)). Power was calculated using an unconditional exact test, with the significance level of the test targeted at 0.05.

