7.2.1. Computation of the Primary Endpoints

The primary analyses will be conducted for participants enrolled under versions 1.0 through 4.0. For each population we will estimate the proportion of participants who experience a systemic allergic reaction (CoFAR Grade 2 and above regardless of tryptase, or CoFAR Grade 1 with elevated tryptase [1.2 x baseline plus 2 ng/ml]) within the 90-minute post-vaccination observation period to either dose of the Pfizer-BioNTech COVID-19 Vaccine and independently the Moderna COVID-19 Vaccine for both the HA/MCD and Comparison populations. These four proportions will be accompanied by their 95% exact (Clopper-Pearson) confidence intervals.

A systemic allergic reaction, categorized as yes or no, is defined as a participant having a reaction to either active dose 1 or active dose 2 (categorized as yes) or to neither active dose (categorized as no). Grade 1 systemic allergic reactions will only be categorized as yes if the tryptase is elevated as determined by the VCU lab. If the tryptase cannot be evaluated for a Grade 1 event (i.e. if missing a pre-treatment and/or post-treatment value), the study management team will determine the subjects categorization based on all available data for the subject.

Participants who do not have a systemic allergic reaction to the 1st active dose and missing data for their 2nd active dose will be removed from this analysis (complete case analysis).

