7.2.3. Sensitivity Analyses of the Primary Endpoint

Missingness (not due to allergic reaction) will be evaluated for each vaccine type separately in each age group. If more than 5% of participants are missing their second active dose for either the Pfizer-BioNTech COVID-19 Vaccine or the Moderna COVID-19 Vaccine, a sensitivity analysis using the tipping-point approach will be conducted to assess the robustness of the primary analysis results. This analysis will only be conducted in the vaccine arm(s) with more than 5% missing. Participants missing both active doses will not be imputed. Tipping point analysis explores the influence of missingness on the overall conclusion from statistical inference by positing a wide spectrum of assumptions regarding the missingness mechanism (from less conservative to more conservative). The analysis finds a (tipping) point in this spectrum of assumptions, at which conclusions of the analysis change. After such a tipping point is determined, clinical judgment can be applied as to the plausibility of the assumptions underlying this tipping point.

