Participants with missing data for their 2nd active dose because of a systemic allergic reaction to their 1st active dose (inherent missingness given the current design) will be examined using an extreme case scenario (replacement of all 2nd active dose missing by either yes or no). If the results from this extreme case scenario differs and if there is at least 10 systemic allergic reactions in the 1st active dose a tipping point analysis will be conducted.

Notes

The same analysis will be repeated for the Moderna COVID-19 Vaccine.

Objective (priming)

Assess the difference in proportions of participants with systemic allergic reactions after the second Pfizer-BioNTech COVID-19 Vaccine dose (not placebo arm) versus the first vaccine dose within the placebo arm in the HA/MCD population.

Endpoint

The proportion of participants who experience a systemic allergic reaction (CoFAR Grade 2 and above regardless of tryptase, or CoFAR Grade 1 with elevated tryptase [1.2 x baseline plus 2 ng/ml]) within the 90-minute post-vaccination observation period to the second dose conditional on no systemic allergic reaction to the first dose in the Pfizer-BioNTech COVID-19 Vaccine arm and the first active dose in the Placebo- Pfizer-BioNTech COVID-19 Vaccine arm.

Model Specification

- Endpoint is as defined above.
- Endpoint will be analyzed using Barnard's unconditional exact test.

Model Checking & Diagnostics

This analysis will not be carried out if there are no systemic allergic reactions in the 1st dose among the placebo arm and/or 2nd dose among the Pfizer arm.

Model Results Presentation

Proportions, 95% exact unconditional confidence intervals and p-value will be presented for the 1st dose among Placebo & Pfizer and 2nd dose among the Pfizer arm.

Placebo & Pfizer-BioNTech COVID-19 Vaccine (1st)

Pfizer-BioNTech COVID-19 Vaccine (2nd)

Placebo + Pfizer	placebo	1 st	2 nd
Pfizer	1 st	2 nd	

SAS Code

```
*** Priming;
proc freq data = d_1;
  title "Priming";
  where group = 'HA/MCD' &
    ((dose = 'D1' & Placebo = 'Yes') | (dose = 'D2' & Placebo = 'No'));
  tables dose*resp / riskdiff;
```

```
exact riskdiff barnard;
run;
```

Supportive Statistical Analyses

If there is an issue with the calculation of the Barnard's Exact Unconditional Test, we will perform a univariate logistic regression.

```
*** Priming (Sensitivity);
proc genmod data = d_1;
  title "Priming (Sensitivity)";
  where group = 'HA/MCD' &

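### SAP 7.2.3 assures no primary sensitivity analysis for dose-1 reactors who are not scored as events but miss dose 2 because of the reaction

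*SAP*

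**What the plan says.** **Who may miss dose 2.** Protocol 6.5 stops dose 2 after a Grade 2 or higher reaction, or a Grade 1 reaction with raised tryptase, that is at least possibly related to dose 1. It sets no 90-minute limit. After a Grade 1 reaction without mast cell activation, "he/she will receive counseling by a study physician and will be allowed to receive a second dose if he/she so chooses".

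**Who is scored as an event.** The primary endpoint counts only reactions within 90 minutes of injection. SAP 7.2.1 adds: "Grade 1 systemic allergic reactions will only be categorized as yes if the tryptase is elevated as determined by the VCU lab".

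**Who stays in the primary analysis.** SAP 7.2.1 is a complete-case analysis. Participants who "do not have a systemic allergic reaction to the 1st active dose and missing data for their 2nd active dose will be removed". SAP section 4 says of the Per-Protocol sample: "Participants who do not receive a second active vaccination due to experiencing an allergic reaction will be included in the analysis". SAP 7.2 does not name the sample used for the primary analysis.

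**What is checked.** SAP 7.2.3: "Missingness (not due to allergic reaction) will be evaluated for each vaccine type separately in each age group". A tipping-point analysis follows only if more than 5% lack the second active dose of a vaccine.

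**What the SAP does elsewhere.** SAP 7.3.3 takes "Participants with missing data for their 2nd active dose because of a systemic allergic reaction to their 1st active dose" and sets their missing values to all 'yes' and to all 'no', but only in the paired and priming comparisons of doses.

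**The concern.** SAP 7.2.3 has good reason to exclude dose-1 reactors who are already scored 'yes', because dose 2 cannot change their result. As worded, though, the exclusion can also take in reactors scored 'no', whose result still depends on the dose they did not receive. There are two such groups:

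- (a) Grade 1 reactors without raised tryptase who decline dose 2 after counselling.
- (b) Grade 2 or higher reactors whose reaction began after 90 minutes, for whom Protocol 6.5 stops dose 2.

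The protocol gives its own reason to think the missing outcomes may be informative. In section 1.1 it says that "mild reactions induced by the first vaccine dose may constitute risk factors for more severe reactions after the second dose". If that is so, the HA/MCD proportion, and its difference from the comparison population, could be too low. An error in that direction favours the reassuring conclusion the study hopes to reach.

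**Working it through.** **1. The plan's own figures.** Inputs from Protocol 14.7: 1020 HA/MCD and 680 comparison participants per vaccine, true rates 0.01 and 0.0001, no allowance for dropout, and "Power was calculated using an unconditional exact test, with the significance level of the test targeted at 0.05".

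- Expected HA/MCD events: 1020 × 0.01 = 10.2, as in Table 14.7 (10).
- Exact (Clopper-Pearson) interval for 0/1020: upper limit 1 − 0.025^(1/1020) = 0.0036, as stated.
- 10/1020: 0.98% (0.47% to 1.80%), matching the stated 0.005 to 0.018.
- Exact power of the doubled Barnard test: 85.4%, consistent with the stated minimum of 80%.

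The design figures reproduce. The point concerns missing outcomes, not the sample size.

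**2. The rules side by side.** The result depends on what the reaction terms in SAP 4, 7.2.1 and 7.2.3 mean.

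| Dose-1 reaction, dose 2 not given | Score at dose 1 | Terms mean a primary event | Terms mean a reaction that bars dose 2 | Terms mean any such reaction |
|---|---|---|---|---|
| Primary event | yes | kept as 'yes' | kept as 'yes' | kept as 'yes' |
| (a) Grade 1, tryptase not raised, declines | no | removed, counted in check | removed, counted in check | kept as 'no', not counted |
| (b) Grade 2 or higher, after 90 minutes | no | removed, counted in check | kept as 'no', not counted | kept as 'no', not counted |

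If 7.2.1 is read narrowly and 7.2.3 broadly, both groups are removed and not counted. The text allows this, because 7.2.1 speaks of a systemic allergic reaction and 7.2.3 only of an allergic reaction. SAP 7.2.1 is itself unsettled: it equates a systemic allergic reaction with a 'yes', yet also calls an unscored Grade 1 event a systemic allergic reaction.

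**3. The 5% trigger.** 0.05 × 1700 = 85, so more than 85 second doses of a vaccine must be missing, against about 10 expected events. Protocol 14.7 expects very little dropout. Even 80 such participants, if counted, are 80/1700 = 4.7% and would not start the analysis on their own. Evaluating by age group lowers the count in proportion (for the 300 children planned, more than 15).

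**4. Size, on assumed numbers.** The documents do not give the number of people in groups (a) and (b). Assume m = 20, all in HA/MCD, 10 observed events and 0/680 in the comparison population. The difference then equals the HA/MCD proportion.

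| Handling of the 20 | HA/MCD proportion | 95% exact interval |
|---|---|---|
| All 'no' | 10/1020 = 0.98% | 0.47% to 1.80% |
| Removed | 10/1000 = 1.00% | 0.48% to 1.83% |
| 10% would react | 12/1020 = 1.18% | 0.61% to 2.05% |
| All 'yes' | 30/1020 = 2.94% | 1.99% to 4.17% |

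The all-'yes' figure is 15/1020 = 1.47% for m = 5 and 90/1020 = 8.82% for m = 80.

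**5. Direction.** Removal understates the proportion only if these participants' dose-2 risk r satisfies (10 + 20r)/1020 > 10/1000, that is r > 0.01. Keeping them as 'no' understates it for any r above zero.

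**The case against.** The strongest reply is that a consistent reading exists. Protocol 3.2 and 14.2 link a missed second dose to a dose-1 reaction that meets the qualifying criteria, and SAP 7.3.3 treats such gaps as built into the design. That fits mandated stops better than a voluntary refusal. On this reading group (a) is removed, counted in the 5% check and open to the tipping-point analysis. This stands, and it is why a reader who infers a flat contradiction between SAP 4, 7.2.1 and 7.2.3 goes too far. The defect is an undefined term. In addition, the inclusion sentence in SAP 4 governs only the Per-Protocol sample, which the SAP does not assign to the primary analysis. But if the term means a reaction that bars dose 2, group (b) is still outside the check, and on any reading the 5% trigger remains.

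A reader might also infer that these second doses are never tested. The documents do not support that. Once the trigger is met, SAP 7.2.3 rules out imputation only for people lacking both active doses, and the extreme-case replacement in 7.3.3 may reach some of them in the dose comparisons. These reactors can also appear in the by-dose rates (7.2.4), the reasons for stopping treatment (5.1) and the adverse event tables (8.2). None of these is an assured sensitivity analysis of the primary result.

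Two further inferences are not specific to these groups. With the doubled Barnard test, 6 v 0 gives p = 0.056 and 7 v 0 gives p = 0.038, so a single event can decide significance, but that is true of any lost participant. Losing eight of 1020 takes the zero-event upper limit just past 1/275 (1/274.8), but any eight would do so, and 0.00364 still rounds to the stated 0.0036.

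Finally, removal alone hardly moves the estimate, and the protocol says only that mild reactions may be risk factors. Both are correct. The exposure lies in the unobserved second-dose outcomes.

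**Conclusion.** The point holds as a gap in robustness. Dose-1 reactors who are not scored as primary events but miss dose 2 because of the reaction have no defined handling and no assured primary sensitivity analysis. The missingness may be informative and could bias the HA/MCD proportion downward, but neither the bias nor its size is established.

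With 10 events and 20 such participants, the proportion lies between 0.98% and 2.94%. This rests on an assumed count, on all 20 being in HA/MCD, and on the all-'yes' bound, which is not a plausible estimate. If few or none arise, the result does not change. The change is still worth making, because events are expected to be few and the SAP already uses the same bounds for its dose comparisons.

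**What to change.** - In SAP 7.2.3, replace the bracketed exclusion with: *not due to a dose-1 reaction already counted as an endpoint event*. Groups (a) and (b) then enter the 5% check and any tipping-point analysis.
- In SAP 4 and 7.2.1, use one defined term for the reaction, name the sample used for the primary analysis, and state one handling rule for these participants.
- Whether or not 5% is reached, report their number and give the HA/MCD proportion and the population difference with them counted as all 'no' and as all 'yes'.
- Apply the same to SAP 7.3.1, 7.3.2 and 7.3.5, each against its own event definition.

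The cost is SAP wording and two extra result lines per endpoint, with no new data and no change to any clinical rule. The all-'yes' line should be labelled an extreme bound so that it is not read as an estimate.

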5. STUDY PARTICIPANTS

5.1. Disposition of Participants

The disposition of all enrolled participants will be summarized in tables and listed.

The numbers and percentages of participants randomized, in each treatment group and cohort (HA/MCD or Comparison), and completing each scheduled injection, as well as reasons for early termination from the study will be presented. For participants discontinuing study treatment early, the reasons for discontinuing study treatment early will also be presented.

5.2. Demographic and Other Baseline Characteristics

Summary descriptive statistics for baseline and demographic characteristics will be reported for the as-treated sample. Characteristics to be summarized include site, age, race, ethnicity, sex, body weight, and height, and BMI at enrollment. Additionally, cohort assignment (HA/MCD or Comparison) and associated details will also be presented.

6. STUDY OPERATIONS

6.1. Protocol Deviations

Protocol deviations will be listed by site with information such as type of deviation, severity of the deviation (major or non-major), date of occurrence, and the reason for the deviation. Protocol deviations will be summarized in tabular format by type of deviation.

